3.8. Participant retention, adherence and sustainability

The Principal Investigator and study team will exert every effort to facilitate participants' completion of all study visits and ensure overall study retention. The following strategies will be implemented to maximize participants' retention and minimize loss to follow-up: a) implementing a proactive retention plan that focuses on building close participant relations and ensuring participant satisfaction, b) giving the opportunities for participants and their families to ask questions and voice any concerns related to their condition throughout the study, c) reinforcing comprehension of the objectives and protocol of the study during study visits or conducting question and answer sessions after each visit, and d) evaluating each likelihood of dropout and implementing appropriate interventions to maintain their interest and motivation to continue participating in the study.

All supervised exercise sessions will be performed in a well-lit and airy room, providing to the participants the opportunity to choose their own music. The training specialists and other study staff will consistently offer support to participants throughout the duration of the study.

During the 12-week intervention period, participants will be required to record their daily sleep and eating times (i.e., exact times of the beginning of the first meal and of the end of the last meal), as well as any potential adverse events in a mobile phone app specifically designed for the study. These data will be revised 2 to 3 times every week, asking the participant for missing records, and will provide insights into their adherence to the prescribed eating window. For participants in the TRE + Exercise group and TRE alone group, each day will be labeled as adherent if the participant meets their self-selected 8-hour (± 30 minutes) eating window. Adherence will then be defined as the percentage of days on which the eating window was met. Finally, we will assess the long-term adherence to the intervention (at the 12-month follow-up). This will allow us to evaluate the sustainability of participants' adherence over an extended period. Attendance will be defined as percentage of exercise sessions attended by the participant (TRE + Exercise

and Exercise alone groups), recorded by the trainers, divided by the actual number of exercise sessions offered (12 weeks x 2 sessions / week = 24). Finally, we will assess the long-term adherence to the intervention (at the 12-month follow-up). This will allow us to evaluate the sustainability of participants' adherence over an extended period.

3.9. Adverse events

The study coordinators and project managers will oversee the collection of data and monitor the frequency of reported adverse events on a weekly basis using the mobile phone app (Tempus: com.nnbi.app_extreme_granada; NNBi2020 S.L., Navarra, Spain). Additionally, participants will complete validated questionnaires that assess gastrointestinal and autonomic symptoms, well-being, eating behavior, sleep quality, stress levels, mood, anxiety, and depression. These questionnaires will offer valuable information on any potential adverse effects and overall health-related outcomes. If a serious adverse event or an unanticipated problem occurs, the study coordinators will immediately notify both the principal investigators and the medical staff. Subsequently, a collective decision will be made and, if needed, the ethics committee will be properly informed. Moreover, appropriate measures will be taken to address and manage the reported event effectively.

3.10. Data management

Data collected will be directly entered into REDCap (Research Electronic Data Capture), a secure web-based platform specifically designed to create and manage research-related databases and surveys. This platform will ensure data security and confidentiality. For any data not recorded in REDCap, strict access control measures will be implemented to securely store the data on university computers, maintaining confidentiality and data integrity.

To ensure data quality and integrity, regular quality control checks will be conducted to identify any potential data anomalies, such as missing data or forms, data that falls outside the expected range, erroneous data entries, illogical dates over time, data inconsistencies across different forms and study visits, and incomplete fields on completed forms without a valid explanation for the missing data. Any identified issues will be promptly reviewed and addressed by the data monitoring committee to ensure the accuracy and reliability of the data. The data monitoring committee will be independent from the sponsor. There are no auditing procedures planned.

3.11. Patient and public involvement

TEMPUS will stimulate patient and public involvement throughout the entire process. Potential participants have actually been involved in the preparation of the intervention and in the development of the mobile app, organization of the outcome measures, as well as are helping in the recruitment of new participants. Once we have the results ready, we will actively involve the participants in the reporting and advocacy of the study results.

4. Statistical Analysis Plan

4.1. Randomization and blinding

We expect to recruit and randomize ~184 participants using both stratification and permuted blocks with random block sizes, after completing the pre-intervention measurements. Randomization will be stratified based on sex (men-women), resulting in 2 strata. Prior to the beginning of the trial, randomization lists will be generated for each strata. The block sizes will be randomly determined, with allowable sizes of 4 and 8.

Within each block, random selection will be used to assign participants to one of the four possible groups (i.e., UC, TRE, Exercise or TRE + Exercise) using a parallel design with a 1:1:1:1 allocation ratio. The sequential assignment of participants will follow the predetermined randomization list specific to their strata. The utilization of random block sizes ensures that the next assignment cannot be predicted. Stratification by sex ensures that the intervention groups will be balanced for this important characteristic. Blinding procedures will be rigorously applied to all personnel responsible for assessing primary outcomes, specifically hepatic fat depots and other ectopic fat depots derived from MRI. This blinding will also extend to those analyzing cardiometabolic risk factors, conducting glucose monitoring, examining fecal microbiota, evaluating physical activity and sedentary time, as well as those engaged in the statistical analysis of data. Conversely, personnel responsible for other measurements and intervention administration will not be blinded to the group assignment (open-label). Participants will receive clear information about the group they will be assigned to, along with details about the study hypotheses. In order to ensure practicality and feasibility, and based on previous research experience (64–66), the study will be conducted in successive waves of participants, each of them including a maximum of 16 participants.

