The study primary outcome will be changes from baseline to 12 weeks in hepatic fat. Secondary outcome variables include changes 12 weeks to 12 months in hepatic fat, changes from baseline to 12 weeks and change from 12 weeks to 12 months in other specific fat depots (i.e., visceral and abdominal subcutaneous adipose tissue, pancreatic fat and mid-thigh intermuscular and intramuscular adipose tissue), elastography (i.e., liver stiffness, liver steatosis and liver viscosity), anthropometry and body composition (i.e., fat mass and fat free mass, bone mineral density and content and skeletal muscle tissue – via MRI-), cardiometabolic markers (i.e., fasting glucose, fasting insulin, hemoglobin A1c and the homeostatic model of assessment for insulin resistance [HOMA-IR], lipid profile, liver markers, blood pressure and inflammatory biomarkers), 24h, diurnal and nocturnal mean glucose (via CGM), fecal microbiota, sleep and physical activity patterns,

Version: 2

psychological outcomes (i.e., depression, stress and anxiety), quality of life, dietary habits and eating behaviour assessment, and physical fitness (i.e. cardiorespiratory fitness, lower muscular strength, upper muscular strength and walking speed). After the screening examination and the 2-week lead-in period, pre-intervention assessments will be held within 3 face-to-face sessions:

Day 1: participants will perform physical fitness tests and will be required to complete several web-based questionnaires. These questionnaires will gather information on several outcomes such as quality of life, sleeping patterns, psychological status and eating behaviour. Dietary intake will be also assessed by qualified nutritionist where participants will be asked to provide the first 24-hour recall detailing their food consumption.

Day 2: fasting venous blood samples will be collected at the San Cecilio University Hospital (Granada, Spain). Thereafter, anthropometric and body composition measurements will be conducted at the Sport and Health University Research Institute (iMUDS - 300 meters apart). Finally, oral glucose tolerance tests will be also conducted as part of the glycaemic assessment.

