Day 3: magnetic resonance imaging (MRI) and elastography will be performed in the San Cecilio University Hospital by the TEMPUS' medical staff (Granada, Spain). To ensure consistency and standardization during the assessment, participants will be instructed to maintain a fasting period of 8-10 hours prior to the appointment, during which they will be advised to consume only water and abstain from solid food or other beverages. In addition, participants will be advised not to consume alcohol or diuretics 24 hours before the test and to avoid stimulants like caffeine for 12 hours before the test.

Table 2. Overview of the study outcomes.

Outcomes	Pre-Intervention	Mid-term	Post-Intervention	12-month follow-up
Primary outcome				
Hepatic fat	✓		✓	✓
Secondary outcomes				
Ectopic fat depots	✓		✓	✓
Anthropometry and body composition	✓	✓	✓	✓
Cardiometabolic markers	✓		✓	✓
Glycaemic control	✓		✓ *	
Fecal microbiota	✓		✓ *	
Plasma and fecal metabolomics	✓		✓	
Sleep and physical activity	✓		✓ *	✓
Psychosocial	✓		✓	
Quality of life	✓		✓	✓
Eating behavior and dietary habits	✓		✓	✓
Physical Fitness	✓		✓	

*Assessment will be conducted during the last 2 weeks of the intervention.

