12. Change in liver stiffness (baseline, 12 weeks, and 12-month follow-up). The quantification of liver stiffness will be assessed using shear wave elastography with a Canon Aplio i800.
13. Change in liver steatosis (baseline, 12 weeks, and 12-month follow-up). The quantification of liver steatosis will be assessed using attenuation imaging coefficient with a Canon Aplio i800.
14. Change in liver viscosity (baseline, 12 weeks, and 12-month follow-up). The quantification of liver viscosity will be assessed using shear wave dispersion with a Canon Aplio i800.

ANTHROPOMETRY AND BODY COMPOSITION:

15. Change in body weight (baseline, 6 weeks, 12 weeks, and 12-month follow-up). Body weight will be measured by a digital scale.
16. Change in waist circumference (baseline, 6 weeks, 12 weeks, and 12-month follow-up). Waist circumference will be assessed by measuring tape following the procedures outlined by the

International Society for the Advancement of Kinanthropometry.

17. Change in hip circumference (baseline, 6 weeks, 12 weeks, and 12-month follow-up). Hip circumference will be assessed by measuring tape following the procedures outlined by the International Society for the Advancement of Kinanthropometry.
18. Change in neck circumference (baseline, 6 weeks, 12 weeks, and 12-month follow-up). Neck circumference will be assessed by measuring tape following the procedures outlined by the International Society for the Advancement of Kinanthropometry.
19. Change in calf girth (baseline, 6 weeks, 12 weeks, and 12-month follow-up). Calf girth will be assessed by measuring tape following the procedures outlined by the International Society for the Advancement of Kinanthropometry.
20. Change in fat mass (baseline, 6 weeks, 12 weeks, and 12-month follow-up). Fat mass will be assessed by bioelectrical impedance analysis (BIA).
21. Change in fat-free mass (baseline, 6 weeks, 12 weeks, and 12-month follow-up). Fat-free mass will be assessed by BIA.
22. Change in bone mineral density and content (baseline, 6 weeks, 12 weeks, and 12-month follow-up). Bone mineral density and content will be assessed by dual-energy X-ray Absorptiometry (DXA).

BLOOD PRESSURE:

23. Change in systolic blood pressure (baseline, 6 weeks, 12 weeks, and 12-month follow-up). Systolic blood pressure will be assessed by blood pressure monitor.

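### Read literally, the protocol's blinding rule leaves the three ultrasound elastography outcomes open-label, although they are operator-acquired and blinding them would cost little

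*Protocol*

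**What the plan says.** Protocol version 2, section 4.1, sets the rule in three steps. First (the sentence closes with the word MRI, left off here for length): "Blinding procedures will be rigorously applied to all personnel responsible for assessing primary outcomes, specifically hepatic fat depots and other ectopic fat depots derived from". Second, "This blinding will also extend to those analyzing cardiometabolic risk factors, conducting glucose monitoring, examining fecal microbiota, evaluating physical activity and sedentary time", and also to the statistical analysts. Third, everything not listed: "Conversely, personnel responsible for other measurements and intervention administration will not be blinded to the group assignment (open-label"). The paragraph adds for participants: "Participants will receive clear information about the group they will be assigned to, along with details about the study hypotheses".

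Elastography appears in four places in the current documents:

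- Protocol 3.4 lists it as a secondary outcome, separate from the fat depots and the cardiometabolic markers: "elastography (i.e., liver stiffness, liver steatosis and liver viscosity").
- Protocol 3.4, Day 3: "magnetic resonance imaging (MRI) and elastography will be performed in the San Cecilio University Hospital by the TEMPUS' medical staff".
- Protocol 3.5, headed as the primary outcome, describes the ultrasound measures directly after the MRI measure.
- SAP 5.1 gives it its own group, items 12 to 14, at baseline, 12 weeks and 12 months. Item 13 reads: "The quantification of liver steatosis will be assessed using attenuation imaging coefficient with a Canon Aplio i800".

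**The concern.** Elastography readings depend on the person holding the probe, who chooses where and when to measure and which acquisitions to keep. An operator who knows the allocation can shift the values without intending to. Item 13 also measures the same concept as the primary outcome by another technique, so readers will naturally use it to corroborate the MRI result. That support is weaker if MRI was assessed blind and ultrasound was not.

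The rule also seems not to have followed the outcome list. The 4.1 paragraph in protocol version 2 is the same as in version 1, yet version 2 added elastography to the secondary outcomes in 3.4. (Version 1 of the SAP already had a single hepatic elasticity item; version 2 split it into three.)

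At stake are the post-randomization values of three secondary outcomes. Baseline readings are safe because randomization follows the pre-intervention measurements.

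**Working it through.** **Text check.** The plan states no figure on this point, so the first step is to set each elastography measure against each entry in 4.1.

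| Blinded category in 4.1 | Stiffness (item 12) | Steatosis (item 13) | Viscosity (item 14) |
|---|---|---|---|
| Primary outcome and ectopic fat from MRI | no | arguable by concept; not MRI | no |
| Cardiometabolic risk factors | listed separately in 3.4 | listed separately | listed separately |
| Glucose monitoring, microbiota, physical activity | no | no | no |

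Stiffness and viscosity fit no entry. Steatosis fits only if the primary-outcome phrase is read without its restriction to MRI. All three therefore fall under the open-label remainder on a literal reading.

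**Illustration of size.** The documents give no bias, so the shift b (in SD units) is assumed.

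Inputs:
- 46 per arm and 20% dropout (Protocol 4.2), so n = 46 × 0.8 = 36.8, about 37.
- Two-sided 5% test (SAP 3.1).
- Pre-post correlation r: the plan's 0.8 is stated for hepatic fat, so applying it to elastography is an assumption. r = 0 (no gain from baseline adjustment) is taken as the other end.

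Formulas: SE = √(2/n) × √(1 − r²); z = b/SE; false-positive rate = [1 − Φ(1.96 − z)] + Φ(−1.96 − z).

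- r = 0: SE = √(2/36.8) = 0.233.
  - b = 0.1: z = 0.43, rate 7.1%.
  - b = 0.2: z = 0.86, rate 13.8%.
- r = 0.5: SE = 0.233 × 0.866 = 0.202.
  - b = 0.1: rate 7.9%.
  - b = 0.2: rate 16.8%.
- r = 0.8: SE = 0.233 × 0.6 = 0.140.
  - b = 0.1: z = 0.71, rate 11.0%.
  - b = 0.2: z = 1.43, rate 29.8%.

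**Effect of the planned gate.** SAP 5.2 allows pairwise comparisons only after a significant global test. I simulated a four-arm F test at 5% followed by TRE + Exercise versus UC (37 per arm, 200,000 replicates), with the shift in the combined arm only, graded across the arms, or equal in all three intervention arms. At r = 0.8 the rate is about 5% for b = 0.1 and 16% to 19% for b = 0.2. At r = 0.5 it is about 3% and 8% to 9%. With no shift, the gated rate for this one comparison is about 2%, so the gate lowers the level but the shift still raises the rate well above its unbiased value.

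**The case against.** The strongest reply is that no sentence says elastography is unblinded. Section 3.5 places it under the primary-outcome heading, 4.1 blinds all who assess primary outcomes, and the MRI and the ultrasound are done on the same day by the same group of medical staff. If those staff are kept unaware for MRI, they may be unaware for ultrasound too. This stands as far as it goes: the status is ambiguous, and open-label is an inference from the residual clause. It does not remove the gap, because 4.1 restricts its primary-outcome blinding to MRI-derived measures and stiffness and viscosity have no place on the list.

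The bias is also hypothetical, and the upper figures rest on a correlation borrowed from another outcome and on ignoring the global test. That is correct, which is why a range is shown.

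Three stronger readings are tempting and not supported:

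- *That an ultrasound reading by an unblinded operator is worthless as support for MRI.* Possible bias weakens corroboration; it does not cancel it.
- *That participants are told which programme is expected to win.* Section 4.1 says only that they receive details of the hypotheses. The consent material is not available here and may already be neutral. Explaining what a trial tests is part of consent, and how much to disclose is a debatable trade-off. Participants cannot be blinded to their arm, so withholding hypotheses would protect only partly, and it would not change an operator's reading.
- *That disclosure will drive usual-care participants to drop out.* Nothing in the documents shows this. That arm receives monthly education sessions, and Protocol 3.8 sets out a retention plan.

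**Conclusion.** The point holds in a limited form. Under the wording of Protocol 4.1, three prespecified secondary outcomes default to open-label measurement, and 3.5 and 4.1 do not agree clearly on their status. Only the 12-week and 12-month values are exposed. The primary outcome is assessor-blinded, and the main analyst works with coded arms.

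The size cannot be known from the documents. The ungated rates of about 7% to 11% (0.1 SD) and 14% to 30% (0.2 SD) show how sensitive a 5% test would be; they are not evidence that such a shift will occur. They assume about 37 evaluable per arm, equal variances and a correlation between 0 and 0.8, and the planned gate lowers them. This is a modest weakness that is worth correcting because the correction is cheap.

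**What to change.** In Protocol 4.1, add the acquisition and reading of elastography (SAP items 12 to 14) to the blinded measurements. Withhold allocation from the Day 3 staff who perform it, and ask participants not to reveal their arm at that visit. Align 3.5 with 4.1 so that both say the same about who is blinded for the ultrasound measures. For any post-randomization scans already done, record whether the operator knew the arm and report it.

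The cost is protocol wording and an instruction at the visit. No extra assessor should be needed if the Day 3 staff can be kept unaware of allocation. The documents do not settle that: Protocol 3.9 has medical staff notified of serious adverse events, so some may learn an arm that way. Occasional accidental unblinding should be expected and logged.

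Optionally, and apart from the main point, the sponsor could check that what participants are told about the hypotheses is neutral on which programme is expected to work better. If that text had to be changed, the ethics committee would need to be notified.

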4.2. Sample size

Based on previous findings from a recent trial on the combination of alternate day fasting and exercise on hepatic fat content (67), we anticipate approximately 5.0% reduction in hepatic fat content in the TRE + Exercise group, 2.5% in the TRE group, 2.5% in the exercise group, and no significant change in this outcome in the usual-care group. Assuming a pre-post correlation of 0.8 and a standard deviation of 6 points in the main outcome, we estimate a medium effect size of 0.45. To detect this effect size as statistically significant in a one-way ANOVA with $\alpha = 0.05$ and a power of 0.8, a minimum of 19 patients per group is required. Accounting for subgroup analyses based on sex and a maximum dropout rate of 20%, we will aim to recruit ~46 participants for each trial group, resulting in a total sample size of ~184 participants, with ~92 women included. To ensure a balanced representation of both sexes and maintain an adequate sample size, we will implement several strategies:

- Recruitment Process: A specific recruitment process will be utilized to aim for an equal enrollment of men and women. For each woman recruited, we will encourage her to invite one man to participate in the study. This approach has been successfully employed in our previous intervention studies and has proven effective in achieving a balanced sex distribution (68–70).
- Sample size calculations: Our sample size calculations have taken into account subgroup analyses by sex. We have conservatively estimated a maximum dropout rate of approximately 20%. By considering this dropout rate, we have ensured that our study is adequately powered to detect the specified effect size even if there are differential dropout rates between men and women. For example, if men have a dropout rate of 5% and women have a dropout rate of 15%, our study will still have sufficient power to analyze the data separately in men and women.
- Expected dropout rate: While we have conservatively estimated the maximum dropout rate, we anticipate that the actual dropout rate will be relatively lower and similar between both sexes. This expectation is based on our previous studies and the measures we have to promote participant engagement and adherence (68–70).

4.3. Statistical analysis

The main analyses will consist of the intention-to-treat analyses for the primary and

Version: 2

secondary outcomes using a constrained baseline (meaning baseline adjusted) linear mixed model, which accounts for baseline differences among the study groups. The model will include fixed effects for time (three levels) and treatment (four levels) as well as the unique participant identifier as a random effect, and sex will be included as a covariate. Model assumptions will be checked. In case we detect model violations, we will take appropriated measures by e.g., conducting data transformations. If the global test of significance indicates between-group differences, pairwise comparisons will be explored. Although no adjustments for multiplicity will be performed, family-wise type 1 error rate on the primary outcome will be retained by using a hierarchical analytic approach. The prespecified hierarchical hypotheses will be tested using the prespecified sequence: TRE + Exercise versus UC, TRE versus UC, Exercise versus UC, TRE + Exercise versus TRE, TRE + Exercise versus Exercise and TRE versus Exercise. The main statistical analyses will be performed by an independent researcher ([name]), who is not involved in the recruitment, evaluations, and interventions, and will be performed blinded to the treatment allocation by coding the intervention arms (e.g., A, B, C, D).

It should also be noted that the intervention effect assessments will not only be based on statistical and practical significance (as usually done), but also on a practical benefit approach emphasizing and reporting unadjusted values that are intuitive to human judgment and readily replicable considering the design and methodology of this project.

5. Ethics and dissemination

The study has received ethical approval from the Granada Provincial Research Ethics Committee (CEI Granada - 0365-N-23) and will be performed following the ethical guidelines of the Declaration of Helsinki. Before their inclusion in the study, participants will be required to provide oral and written informed consent, with further details available in the Online Supporting Information.

Results will be presented in peer-reviewed, scientific journals and at international conferences. We aim to publish a main paper with the primary outcome data. Since it is a large study with numerous secondary outcomes, other specific manuscripts on each topic will be published.

6. References

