3.1. Confidence and P values

All statistical tests will be two-tailed. *P* for significance will be set at 0.05 and 95% confidence intervals will be estimated. No adjustment for multiplicity will be made as multiplicity adjustments may be of lesser importance in the case of distinct treatment arms.³ Moreover, only one primary outcome will be defined and other outcomes (i.e., secondary outcomes, and exploratory analyses) will not require adjustment for multiple testing. However, we will include a hierarchical analytic approach for the interventions tested and the primary outcome.

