5.2. Analysis methods

The main analyses will consist of the intention-to-treat analyses for the primary and secondary outcomes using a constrained baseline (meaning baseline-adjusted) linear mixed model, which accounts for baseline differences among the study groups. The model will include fixed effects

for time (three levels) and treatment (four levels) as well as the unique participant identifier as a random effect, and sex will be included as a covariate. Model assumptions will be checked. In case we detect model violations, we will take appropriate measures by e.g., conducting data transformations. If the global test of significance indicates between-group differences, pairwise comparisons will be explored. Although no adjustments for multiplicity will be performed, family-wise type 1 error rate on the primary outcome will be retained by using a hierarchical analytic approach. The prespecified hierarchical hypotheses will be tested using the prespecified sequence: TRE + Exercise versus UC, TRE versus UC, Exercise versus UC, TRE + Exercise versus TRE, TRE + Exercise versus Exercise, and TRE versus Exercise. The main statistical analyses will be performed by an independent researcher ([name]), who is not involved in the recruitment, evaluations, and interventions, and will be performed blinded to the treatment allocation by coding the intervention arms (e.g., A, B, C, D).

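### Sex enters the constrained-baseline model as a plain covariate; adding sex-by-visit would let the stratification factor adjust the change as well as the level, at almost no cost

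*Protocol*

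**What the plan says.** The current protocol (Version 2), section 4.3, describes a constrained-baseline linear mixed model with "fixed effects for time (three levels) and treatment (four levels) as well as the unique participant identifier as a random effect". It then adds that "sex will be included as a covariate". The current SAP, section 5.2, has the same model: "the unique participant identifier as a random effect, and sex will be included as a covariate". Neither text names an interaction of sex with time or with treatment, and neither says that sex is to be a main effect only.

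The primary outcome is the change in hepatic fat from baseline to week 12 (Protocol 3.4; SAP 5.1). Sex is the only stratification factor: "Randomization will be stratified based on sex (men-women), resulting in 2 strata" (Protocol 4.1). Missing data are assumed missing at random and left to the mixed model, with a commitment to reconsider (SAP 5.3).

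On dropout, Protocol 4.2 claims adequate power "even if there are differential dropout rates between men and women" and gives 5% in men and 15% in women as an example. It then says that it expects dropout to be lower than the 20% maximum and similar in the two sexes. The superseded analysis text had separate models for men and women and an attrition model that included sex. The current analysis sections have neither, so the covariate is the only adjustment for sex in the main model.

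**The concern.** When baseline is an outcome in the model, a sex term without a sex-by-visit term moves the whole profile for men or women up or down together. It cannot describe men and women changing by different amounts, yet change is the endpoint.

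Two things could follow if the sexes do change differently. The unfitted part of the gap goes into the residual, so the model reports a larger standard error than the stratified design delivers. And if one sex is lost more from one arm than from another, the model carries the wrong sex gap into the missing week-12 values, and the treatment contrast shifts.

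This is a separate matter from a treatment-by-sex interaction. The sex-by-visit term is common to all arms and leaves the estimated treatment contrast unchanged in meaning.

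**Working it through.** **Plan's own figure.** The plan gives no standard error for this contrast. Its only related figure is the minimum of 19 per group, "in a one-way ANOVA with $\alpha = 0.05$ and a power of 0.8". Reading the effect size of 0.45 as Cohen's f, with four groups, I get 15 per group; 19 gives power 0.909. The stated figure is on the safe side and does not bear on this point.

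**Inputs from the documents.** SD 6, pre-post correlation 0.8, expected changes 0 / -2.5 / -2.5 / -5 points, about 46 per arm (23 per sex), "1:1:1:1 allocation ratio", and the example dropout of 5% in men and 15% in women.

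**Assumptions not in the documents.** D, the change in the sex gap from baseline to week 12, set at 0 to 3 points and first taken as equal in all arms; dropout rates that differ by arm; in the simulation, a 2-point baseline gap, the same D at month 12, and half the week-12 effect remaining at month 12.

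**Standard error, analytic check (two visits, complete data).** With equal variances at the two visits, generalised least squares fits a gap halfway between the true ones, leaving -D/2 at baseline and +D/2 at week 12. Given baseline, the unfitted part at week 12 is D/2 + 0.8 × D/2 = 0.9D. With equal numbers of men and women this adds (0.9D)²/4 to a conditional variance of 36 × (1 - 0.64) = 12.96.

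- D = 1: 0.2025 / 12.96 = 1.6% in variance, 0.8% in SE
- D = 2: 0.81 / 12.96 = 6.3% in variance, 3.1% in SE
- D = 3: 1.8225 / 12.96 = 14.1% in variance, 6.8% in SE

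**Standard error, simulation.** Reported SE of TRE + Exercise versus usual care at week 12, with 5%/15% dropout in every arm. Each cell gives constant sex versus sex-by-visit. Treatment-by-time at follow-up was included in both fits.

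| D | Two visits, unstructured covariance | Three visits, random intercept (as planned) |
|---|---|---|
| 0 | not tabulated | 0.789 vs 0.790 |
| 1 | 0.793 vs 0.786 (+0.9%) | 0.794 vs 0.790 (+0.5%) |
| 2 | 0.810 vs 0.785 (+3.3%) | 0.806 vs 0.790 (+2.0%) |
| 3 | 0.841 vs 0.785 (+7.1%) | 0.826 vs 0.790 (+4.6%) |

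With no dropout, the empirical SE was 0.753 for both models at every D; only the reported SE differed. For a 2.5-point contrast at the two-sided 5% level, approximate power is Φ(2.5/SE - 1.96). It is 0.886 with SE 0.790 and 0.873 with SE 0.806 (D = 2, random intercept).

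**Bias with the constant sex term (points, TRE + Exercise versus usual care).** The sign is for women improving less than men; negative means that the benefit looks too large.

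| Dropout | D = 1 | D = 2 | D = 3 |
|---|---|---|---|
| 5% men, 15% women in every arm | about 0 | about 0 | about 0 |
| Women 30% in TRE + Exercise, 5% in usual care | -0.07 | -0.14 | -0.21 |
| Usual care men 15%, women 5%; TRE + Exercise men 5%, women 25% | -0.09 | -0.17 | -0.24 |
| Extreme: usual care men 40%, women 0%; TRE + Exercise men 0%, women 40% | -0.25 | -0.48 | -0.70 |

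Coverage in the extreme case is 93.5%, 91.1% and 88.4%; in the row above it, 95% or a little more. With sex-by-visit the bias is within simulation noise (-0.01 to -0.03) and coverage is about 95%.

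**If D differs by arm.** Under the 30% versus 5% dropout pattern, with D = 0/1/1/2 for usual care, TRE, Exercise and the combination, the bias is -0.145 without sex-by-visit and -0.079 with it. With D = 2 in the combined arm only, it is -0.148 and -0.117.

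**The case against.** The strongest reply is that the documents do not forbid a sex-by-visit term. They say covariate, and the same sentence also omits treatment-by-time, without which the model has no week-12 contrast. The formula may simply be incomplete. That stands: the constant gap is the literal reading and not a declared choice. It is also a reason to write the term down before the data are analysed.

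Next, nothing in the documents says that the sexes will change by different amounts over 12 weeks. The sex dimorphism that the protocol mentions concerns the development of the disease, and a constant term can absorb a stable difference. A D of 2 to 3 points is about as large as the whole effect planned for TRE or Exercise alone, and a D common to all arms would have to appear in usual care too, where no significant change is anticipated. This stands, and it makes the upper rows of the range less likely.

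A reader might infer that the intervals for all six contrasts are too wide, or that sex-related dropout goes uncorrected. The documents support neither. The widening exists only if D is not 0. The sex term and each participant's own baseline already deal with a stable gap. The plan's 5%/15% example, applied to every arm, gives no bias, and the plan itself expects similar dropout by sex. The plan also commits to checking model assumptions and to revisiting missing at random, although neither commitment names this term.

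**Conclusion.** On the literal reading, the sole stratification factor adjusts the level of hepatic fat but not its change, and the plan should say otherwise. The expected consequence is modest. For D = 1, 2 and 3 the reported standard error is conservative by about 0.5-1%, 2-3% and 5-7%, the lower figures belonging to the planned three-visit random-intercept model. Bias needs two conditions together: a gap that changes, and a sex pattern of dropout that differs between arms. In moderate assumed cases it is about -0.1 to -0.25 points against a planned 5-point effect. If D itself differs by arm, the sex-by-visit term removes only part of that bias; the remainder is a treatment-by-sex question. If D = 0 nothing is lost. All of this rests on assumed values of D and of arm-specific dropout. It is a cheap improvement and not an error that invalidates the analysis.

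**What to change.** In Protocol 4.3 and SAP 5.2, replace the clause on sex with: *sex and the sex-by-visit interaction will be included as fixed effects*. Apply it to the primary outcome and to the secondary outcomes analysed with this model.

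The cost is one sentence in each document and one extra parameter per follow-up visit, so two for hepatic fat (week 12 and month 12). No new data are needed. If the gap turns out constant, the price in precision is negligible: SE 0.790 against 0.789 with 5%/15% dropout in every arm. Under the extreme assumed dropout pattern it is somewhat larger (0.852 against 0.838).
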